7.1.8. Pregnancy

Any pregnancy for the partner of a study participant must be reported on the Partner's Pregnancy Report Form within 24 hours and emailed to the RADIUS Pharmacovigilance Department at [contact]. Every effort should be made to gather information regarding the

pregnancy outcome. It is the responsibility of the Investigator to obtain this information within 30 calendar days after the initial notification and approximately 30 calendar days postpartum.

In subjects who have partners of childbearing potential, the subject and his partner should abstain from sexual intercourse, or use highly effective contraceptive measures (e.g., oral contraceptive and condom, IUD and condom, or diaphragm with spermicide and condoms; other forms of contraception must be approved by a Medical Monitor) when engaging in sexual intercourse throughout the study, and for at least 90 days after the last dose of abaloparatide.

7.1.9. Regulatory Agency, Institutional Review Board, Ethics Committee and Site Reporting

The Sponsor and/or the clinical contract research organization (CRO) are responsible for notifying the relevant regulatory authorities/US central IRBs/EU central IEC committees of related, unexpected SAEs.

The Investigator is responsible for notifying the Sponsor, CRO, and local IRB/IEC, or the relevant local regulatory authority of all SAEs that occur at his or her site as required.

If a death occurs during the study or within 30 days after Month 12/Early Termination visit (Visit 8), and it is determined to be related either to a study procedure or a study drug, the Investigator or his/her designee must notify the Sponsor and will communicate that information to the IRB/IEC within one business day of knowledge of the event. The contact may be by phone or email.

7.2. Study Completion and Post-Study Treatment

The Investigator must provide follow-up medical care for all subjects who are prematurely withdrawn from the study due to an adverse event or must refer them for appropriate ongoing care.

7.3. Lost to Follow-up

For subjects whose status is unclear because they fail to appear for study visits without stating an intention to discontinue or withdraw, the Investigator should show "due diligence" by documenting in the source documents steps taken to contact the subject, e.g., dates of telephone calls, registered letters. A subject should not be formally considered lost to follow-up until multiple attempts to contact the subject have been made, including at least 2 attempts to reach the subject by phone followed by a certified letter sent to the subject's last known mailing address.

8. STATISTICAL CONSIDERATIONS

8.1. Statistical and Analytical Plans

A comprehensive SAP will be completed and approved prior to database lock. All statistical tests will be 2-sided with a significance level of 1%, unless otherwise specified.

8.2. Statistical Hypotheses

The primary objective of this study is to evaluate the efficacy and safety of abaloparatide-SC $80 \ \mu g$ per day compared to placebo in men with osteoporosis. The hypotheses to be tested are that abaloparatide is superior to placebo, and that the safety profile of abaloparatide-SC in osteoporotic men is similar to that of abaloparatide-SC in postmenopausal women with osteoporosis.

8.3. Analysis Datasets

8.3.1. Populations for Analysis

The primary population for all efficacy analyses will be the Intention-to-Treat (ITT) Population, which is defined as all subjects randomized into this study. The primary population for safety analyses will be the Safety Population, defined as all subjects who received at least one dose of study medication. The Per-Protocol (PP) Population will include all ITT subjects who did not have any significant protocol deviations and will be used for supportive analyses. The criteria for the exclusion from the PP Population will be appropriately documented prior to database lock and treatment unblinding.

8.4. Description of Statistical Methods

8.4.1. General Approach

Analyses will be presented by treatment group (abaloparatide-SC and placebo) and overall, when appropriate. Baseline is defined as the last value obtained prior to the first dose of study medication.

For categorical data, summary tabulations of the number and percentage of subjects within each category of the parameter will be presented. For continuous data, the number of subjects, mean, median, standard deviation (SD), minimum, interquartile range (Q1 and Q3), and maximum will be presented.

8.4.2. Analysis of the Primary Efficacy Endpoint(s)

The primary efficacy endpoint will be the percent change in lumbar spine BMD from baseline to 12 months. The analyses will be based on the ITT Population.

The missing data from this study will be reviewed carefully to evaluate any missing data patterns. As this study was not designed to systematically collect data from subjects who discontinue treatment early, the "retrieved dropouts" approach for handling missing data is not applicable for this study. To appropriately address the possibility of data missing not at random, the primary analysis will be based on a pattern-mixture model (PMM) analysis with multiple

imputation using the wash-out imputation method. This method uses sequential regression and wash-out imputation methodology to impute missing values after a subject's discontinuation from the study. The missing primary endpoint values for subjects in the abaloparatide-SC group will be imputed with the observed baseline and data from the placebo group; no intermediate values from the abaloparatide-SC group will be used in the imputation for the abaloparatide-SC group. For subjects in the placebo group, intermediate observed values from the completers in the placebo group will be used while imputing missing values during the 12-month Treatment Period. The PROC MI methodology for imputation of monotone missing data patterns will be used to impute the outcome variables at consecutive visits in a sequential (chain) manner. Each of these imputed datasets will be analyzed using analysis of covariance (ANCOVA) with treatment and DXA instrument manufacturer as fixed effects and the baseline lumbar spine BMD as a covariate. Results from all imputed datasets will be combined using PROC MIANALYZE for overall statistical inference. The statistical tests will be 2-sided comparing abaloparatide-SC to placebo; 99% CIs will be presented together with the estimated p-values.

As a sensitivity analysis, the primary efficacy endpoint will also be analyzed using a Mixed Model for Repeated Measures (MMRM) analysis. The MMRM model will include the fixed effects of treatment, DXA instrument manufacturer, visit, and treatment-by-visit interaction, with the baseline lumbar spine BMD as a covariate. For the MMRM model, an unstructured variance-covariance matrix shared between the 2 treatment groups will be used to model the within-subject errors over the visits. The treatment comparison will be obtained by testing the contrast (difference in least squares mean) between the 2 treatment groups at Month 12 (Visit 8). The statistical tests will be 2-sided comparing abaloparatide-SC to placebo; 99% CIs will be presented together with the estimated p-values.

Sensitivity analyses for addressing the effect of the COVID-19 pandemic and supportive analyses using the last observation carried forward (LOCF) method to impute missing data will also be conducted.

8.4.3. Analysis of Secondary Endpoint(s)

The key secondary efficacy endpoints are:

- Percent change from baseline in total hip BMD at 12 months
- Percent change from baseline in femoral neck BMD at 12 months

Additional secondary efficacy endpoints are:

- Percent change from baseline in:
 - Lumbar spine BMD at 3 and 6 months
 - Total hip BMD at 3 and 6 months
 - Femoral neck BMD at 3 and 6 months
 - Ultra-distal radius BMD at 3, 6, and 12 months
 - Distal one-third radius BMD at 3, 6, and 12 months

- Log ratio of post-baseline over baseline in:
 - s-PINP at 1, 3, 6, and 12 months
 - s-CTX at 1, 3, 6, and 12 months
- Proportion of subjects experiencing BMD gains from baseline of > 0%, > 3%, and > 6% at the lumbar spine, femoral neck, and total hip at 3, 6, and 12 months
- Incidence of new clinical fractures at 12 months
- Proportion of subjects converting from the categories of osteoporosis to osteopenia or to normal at 12 months, where:
 - Osteoporosis is defined as lumbar spine or total hip BMD T-score \leq -2.5.
 - Osteopenia is defined as one of the following:
 - \circ Lumbar spine > -2.5 and total hip BMD T-score > -2.5 and < -1.0
 - \circ Lumbar spine > -2.5 and < -1.0 and total hip BMD T-score > -2.5
 - Normal is defined as lumbar spine and total hip BMD T-score \geq -1.0.
- The percent change in total hip and femoral neck volumetric BMD as measured by QCT from baseline to 12 months. QCT will be performed in a subset of subjects at a selected number of study sites.

Analyses of the primary and key secondary endpoints will follow a fixed-sequence testing approach to control the overall Type 1 error rate at the 2-sided significance level of 1%. To claim statistical significance at the 2-sided level of 1%, the following 3 fixed-sequence tests will be performed in sequential order. At any step of the sequential testing, if the treatment difference is not statistically significant at the 1% level then all the subsequent comparisons following the fixed sequence cannot be claimed statistically significant.

- 1. Percent change from baseline in BMD at the lumbar spine at 12 months
- 2. Percent change from baseline in BMD at the total hip at 12 months
- 3. Percent change from baseline in BMD at the femoral neck at 12 months

P-values for treatment comparisons of all other efficacy endpoints will be generated to support the study findings without any adjustments for multiplicity.

The analyses of the key secondary BMD endpoints will be performed using a PMM analysis with multiple imputation using the wash-out imputation method similar to the analysis for the primary efficacy endpoint, as stated in Section 8.4.2, with the appropriate baseline covariate. Sensitivity analyses using MMRM models, sensitivity analyses for addressing the effect of the COVID-19 pandemic, and supportive analyses using the LOCF method, as with the primary efficacy endpoint, will also be conducted.

The bone formation marker, s-PINP, and the bone resorption marker, s-CTX, will be analyzed based on the ratio of the post-baseline value relative to the baseline using a natural log transformation at each visit. The analysis will use a PMM analysis with multiple imputation using the wash-out imputation method similar to that described in Section 8.4.2.
Percent changes from baseline in BMD over time will be summarized using descriptive statistics by visit for each treatment group.

The bone formation marker, s-PINP, and the bone resorption marker, s-CTX, will be summarized descriptively by treatment group, with values, changes and percent changes from baseline, geometric mean values, and geometric mean values relative to baseline at each visit.

A BMD responder analysis by visit will be performed for those subjects who have both baseline and the relevant post-baseline BMD values. Three categories of BMD response will be evaluated: %BMD increase > 0%, > 3%, and > 6%. The response will be assessed at the lumbar spine, total hip, and femoral neck. Subjects who have BMD increase at all 3 skeletal sites at the same visit will be considered responders, with the primary time point at 12 months. No imputation of missing data will be implemented. The number and percentage of responders in each treatment group will be compared using either the Chi-square test or Fisher's exact test.

Kaplan-Meier estimates for the time to new clinical fracture at 12 months and the hazard ratio (99% CI) will be presented, with treatment comparisons based on the log-rank test.

The number and percentage of subjects for whom disease status (categories as defined in the secondary endpoints listed earlier in this section) has changed from osteoporosis at baseline to osteopenia, normal, or no change at 12 months will be analyzed using the Chi-square test.

The percent change from baseline in total hip and femoral neck volumetric BMD (vBMD) at 12 months, as measured by quantitative CT will be analyzed using a similar ANCOVA model as stated in Section 8.4.2.

The primary analyses of the secondary efficacy variables will be based on the ITT Population and will be repeated using the PP Population.

Subgroup analysis (e.g., age, geography, FRAX, prior fracture, and baseline BMD, s-PINP, testosterone, and estradiol levels) may be performed. Details of the subgroup analyses will be described in the SAP.

8.4.4. Pharmacokinetic Analyses

A population PK analysis will be performed on the sparse plasma concentration data of abaloparatide as described in the Pharmacometric Analysis Plan. This analysis may be expanded to include a population PK/exposure-response analysis of the percent change in BMD from baseline over time.

8.4.5. Safety Analyses

Unless otherwise specified, safety analyses will be conducted using the Safety Population and will be descriptive in nature.

Study drug exposure and study drug compliance will be calculated. The duration of study drug exposure, total dose received, and percent compliance will be summarized by treatment group.

All AEs will be coded using MedDRA. The number and percent of subjects who experienced TEAEs will be summarized by MedDRA system organ class (SOC), preferred term, and treatment group. Summaries will also be provided for severe TEAEs, SAEs, TEAEs leading to

study drug withdrawal, drug-related TEAEs (with probable or possible relationship to study drug), and TEAEs by maximum severity (mild, moderate, severe).

The number and percent of subjects who report TEAEs associated with hypercalcemia and hypercalciuria will be summarized by treatment group.

All AEs collected prior to the first dose of study drug will be summarized separately.

A listing of subjects who experience an UADE will be provided.

Descriptive statistics for laboratory data (including serum calcium and albumin), vital signs (including orthostatic blood pressure [BP]), ECGs, Investigator assessment of local tolerance, and subject assessment of local tolerance will be provided by treatment group and visit. For laboratory data, vital signs, and ECGs, absolute results and changes from baseline will be presented. In addition, laboratory test results will be classified as above normal limit, within normal limit, or below normal limit. Laboratory shift frequencies will be tabulated between the Screening Visit and relevant post-baseline visit(s).

For subjects in the abaloparatide-SC group, the anti-abaloparatide antibody assessment in the serum samples for immunogenicity testing will be categorized by 2 outcomes:

- Negative for anti-abaloparatide antibodies
- Positive for anti-abaloparatide antibodies

The number (%) of subjects in the above categories of abaloparatide antibodies will be summarized on Day 1 (Visit 3) and at Month 1 (Visit 4), Month 3 (Visit 5), Month 6 (Visit 6), Month 9 (Visit 7), Month 12 (Visit 8), and the Follow-up Visit scheduled approximately 1 month after the last dose of study medication (Visit 9) using the Antibody Population.

For those subjects with a positive anti-abaloparatide antibody present, the titer level, presence of neutralizing anti-abaloparatide antibodies (negative or positive), and assessment outcomes for cross-reactivity to PTH (negative or positive) and PTHrP antibodies (negative or positive), together with the neutralizing antibody status in subjects that are positive for PTH (negative or positive or positive for the presence of PTH-neutralizing antibodies) or PTHrP (negative or positive for the presence of PTH-neutralizing antibodies), will be summarized by study visit.

The results of antibody analyses will be included in a separate report.

Concomitant medications will be coded using the World Health Organization (WHO) Drug Dictionary and summarized by number and percentage of subjects using each class and preferred drug term by treatment group.

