- 9. Serum calcium and albumin will be measured predose from the standard chemistry panel on Month 1 and Month 6, and from a separate blood draw at Day 1, Month 3 and Month 9 and 4 hours post dose at Day 1, Month 1, Month 3, Month 6, and Month 9.
- 10. A 24-hour urine collection will be collected at Day 1 and Month 3 and will be used for urinary calcium and urinary creatinine measurements. Subjects will discard the first void and begin a 24-hour urine collection on the day prior to the clinic visit.
- 11. If the subject reports that a fracture has occurred, remind the subject to bring X-rays and any medical reports of the fracture to the next clinic visit. Documentation must be obtained on all new fractures that occur during the study. This documentation should be maintained in the source documents.
- 12. Each DXA for a given subject should be performed on the same machine, and if available, preferably by the same technician. For screening purposes, DXA scans of the lumbar spine, total hip, and femoral neck taken up to 35 days prior to the beginning of the Screening Period, with a study-approved scanner, may be used to determine study eligibility.
- 13. The first wrist DXA will be performed prior to study drug administration on Day 1 and should be performed on the same machine, and if available, preferably by the same technician.
- 14. QCT performed in a subset of subjects at selected study sites.
- 15. Samples will be drawn prior to treatment on Day 1, Months 1, 3, 6, 9, and 12, and the Follow-up Visit scheduled at 1 month after the last dose of study medication.
- 16. The subject will maintain a diary of their assessment of local tolerance beginning on Day 2 and continuing through Day 7 in Month 1, and beginning on Day 2 and continuing through Day 7 in Month 9.
- 17. The subject medication diary will be reviewed by study personnel at each study visit to ensure subject compliance.
- 18. AEs and SAEs will be recorded on the case report forms starting from the time of subject entry into the Screening Period (Visit 1) of the study (signed informed consent) until 30 days after the last dose of study medication. All AEs will be followed until resolution or stabilization. Any SAEs that occur at any time after completion of the study, which are considered by the Investigator to be related to study treatment, must be reported to the Sponsor or its designee.

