6.5.3. Immunogenicity Testing

Serum samples for immunogenicity testing will be collected at Day 1 (Visit 3), Month 1 (Visit 4), Month 3 (Visit 5), Month 6 (Visit 6), Month 9 (Visit 7), Month 12 (Visit 8), and the Follow-up Visit scheduled at 1 month after the last dose of study medication (Visit 9). Samples will be tested for the presence of binding anti-abaloparatide antibodies, including determination of antibody titer. Any positive samples will be tested for the potential to neutralize abaloparatide in a cell-based assay. Additionally, positive samples will be tested for cross-reactivity to endogenous PTH and PTHrP. Any subjects who show presence of antibodies at the Follow-up Visit scheduled at 1 month following the last dose of study medication (Visit 9) will be retested at 6-month intervals post-study until antibody status return to negative.

The serum samples for immunogenicity testing will be analyzed and reported separately. All the planned analyses related to the immunogenicity results and antibody status will also be reported separately.

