#### **Antibody Population**

The antibody population will include those abaloparatide-SC treated subjects in the Safety population who have at least one post-baseline anti-abaloparatide antibody assessment.

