## 3.9 Anti-Abaloparatide Antibody Status

At Day 1, Month 1, Month 3, Month 6, Month 9, Month 12/EOT, and Month 13/EOS, for subjects in the abaloparatide-SC group, the anti-abaloparatide antibody (ADA) assessment in the serum samples for immunogenicity testing will be categorized by two outcomes:

- Negative for the ADA (ADA-)
- Positive for the ADA (ADA+)

For those subjects with a positive ADA (i.e, ADA is present), the serum samples will be further assessed for the presence of neutralizing anti-abaloparatide antibodies (NAb), and the results will be categorized by two outcomes:

- Negative for the NAb (NAb-)
- Positive for the NAb (NAb+)

Subjects' ADA status and presence of NAb by Month 12 (ADA-, ADA+/NAb+, ADA+/NAb-, All ADA+) will be defined as follows:

- Subjects will be classified as ADA- if they were ADA- in all post-baseline immunogenicity assessments during the 12 months treatment period.
- Subjects will be classified as ADA+ and NAb+ if they were ADA+ at any post-baseline immunogenicity assessment and NAb+ at any subsequent tests during the 12 months treatment period.
- Subjects will be classified as ADA+ and NAb- if they were ADA+ at any post-baseline immunogenicity assessment and NAb- at all subsequent tests during the 12 months treatment period.

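### SAP 3.9 sets each man's antibody status from post-baseline samples alone, so antibody already present on Day 1 that persists without a titer rise is pooled with treatment-induced antibody

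*Protocol*

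**What the plan says.** **Who is summarised.** Protocol 8.4.5 restricts the categorisation to the active arm: "For subjects in the abaloparatide-SC group, the anti-abaloparatide antibody assessment in the serum samples for immunogenicity testing will be categorized by 2 outcomes", namely negative and positive. The SAP's Antibody Population (section 2.1) is likewise limited to "those abaloparatide-SC treated subjects in the Safety population who have at least one post-baseline anti-abaloparatide antibody assessment".

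**What is collected.** Note 15 to protocol Table 3 makes the Day 1 sample pre-dose: "Samples will be drawn prior to treatment on Day 1, Months 1, 3, 6, 9, and 12". Protocol 6.5.3 adds: "Samples will be tested for the presence of binding anti-abaloparatide antibodies, including determination of antibody titer". Neither section limits sampling to one arm.

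**How status is set.** Under SAP 3.9 a man is ADA- if he was "ADA- in all post-baseline immunogenicity assessments during the 12 months treatment period". One positive post-baseline result puts him in ADA+, with a further split by neutralising antibody. Day 1 status and titer do not appear in the rule.

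**What is done with Day 1 and titer.** Protocol 8.4.5 and SAP 4.5.4 tabulate the number positive on Day 1 beside the later visits, summarise titer by visit, and SAP 4.5.4 lists all antibody data for the active arm.

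**Where status is used.** Baseline tables (SAP 4.2), the MMRM comparisons of lumbar spine, total hip and femoral neck BMD (4.3.1 and 4.3.2), exposure and compliance (4.5.1), and adverse events including those of special interest (4.5.3).

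**The concern.** An analysis by antibody status is usually read as asking what happens to men who mount a response to the drug. The rule in SAP 3.9 answers a different question: what happens to men who test positive at any time after baseline, whatever the origin of the reactivity. If some men carry reactivity before dosing, the ADA+ group mixes two kinds of men, and every table split by status inherits the mixture.

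The protocol gives some reason not to assume that pre-dose reactivity is nil. Section 1.1 states 76% homology with human PTHrP(1–34) and 41% with PTH(1–34), and section 6.5.3 plans cross-reactivity tests against both endogenous molecules. This does not show that pre-existing antibody occurs.

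The SAP also refers to baseline in comparable safety results. A treatment-emergent adverse event must be new or have worsened after the first dose (4.5.3), and the tables of potentially clinically significant laboratory values and vital signs leave out men already abnormal at baseline (4.5.6 and 4.5.7). Antibody status has a pre-dose sample but no equivalent rule.

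**Working it through.** **Step 1: apply the rule to each possible history.** The last column is the class a man would have if his Day 1 result were used.

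| Day 1 | Post-baseline, to Month 12 | Status under SAP 3.9 | Status relative to Day 1 |
|---|---|---|---|
| Negative | All negative | ADA- | Negative |
| Negative | Any positive | ADA+ | Treatment-induced |
| Positive | All negative | ADA- | Pre-existing, not boosted |
| Positive | Positive, titer raised | ADA+ | Treatment-boosted |
| Positive | Positive, no titer rise | ADA+ | Pre-existing, not boosted |

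Only the last row places a man with no treatment-emergent antibody in ADA+.

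**Step 2: look for the missing step elsewhere.** Neither protocol 8.4.5 nor SAP 3.9 or 4.5.4 contains an induced or boosted category, a titer-rise criterion or a Day 1 to post-baseline shift table. The separate antibody report does not supply one, because SAP 3.2 says it will hold the analyses described in the SAP.

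**Step 3: size.** The documents state no antibody rate, so there is no figure to reproduce. Inputs:
- 150 abaloparatide-SC men (protocol 8.5).
- *b*, the proportion positive on Day 1: assumed 1%, 3% or 5%.
- *q*, the proportion of Day 1 negative men who become positive on treatment: assumed 10% or 45%.

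If every Day 1 positive man tests positive again after baseline:
- proportion classed ADA+ = *b* + (1 − *b*)*q*
- pre-existing share of ADA+ = *b* / [*b* + (1 − *b*)*q*]

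| *b* | Men of 150 | ADA+ at *q* = 10% | Pre-existing share | ADA+ at *q* = 45% | Pre-existing share |
|---|---|---|---|---|---|
| 1% | 1.5 | 10.9% | 9% | 45.6% | 2% |
| 3% | 4.5 | 12.7% | 24% | 46.7% | 6% |
| 5% | 7.5 | 14.5% | 34% | 47.7% | 10% |

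For example, at *b* = 5% and *q* = 10%: 0.05 + 0.95 × 0.10 = 0.145, and 0.05 / 0.145 = 34%.

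These shares are upper bounds on misclassification for the chosen rates. A Day 1 positive man who is negative on all later samples is ADA- and leaves the numerator. One whose titer rises belongs in ADA+ as boosted. At *b* = 0 the share is zero.

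**The case against.** The case for leaving the plan alone has several parts.

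- **Day 1 is not ignored.** The Day 1 count stands in the same table as later visits, titers are summarised by visit, and the listing should let a reader find each man who was positive before dosing. This stands. A reader might infer that the trial could not tell pre-existing from new antibody at all; the documents do not support that. The gap is in the subject-level status and the analyses built on it. Reclassifying from a listing would be post hoc and would lack a prespecified titer rule.
- **ADA+ is not labelled drug-related.** This also stands. A reader might infer that the plan counts pre-existing reactivity as caused by the drug, but both documents say only positive or ADA+. The supported statement is that the two kinds are pooled.
- **Antibody of any origin is a fair exposure to study.** True, and the documents do not show that pre-existing antibody is inert. This is a reason to keep the present split as a second analysis; it does not justify having no baseline-referenced one.
- **The analyses are minor.** They lie outside the fixed testing sequence and are reported separately. This limits the importance of the point but does not remove it, because the presence of antibodies is a named safety endpoint.
- **Placebo adds little.** The omission of placebo is tempting to press as a main defect. The pre-dose Day 1 sample already shows background reactivity in the larger arm, and placebo would mainly add background arising over time. SAP 1.2.3 points to a blind management plan and an operations manual that are not among the documents, so it cannot be seen whether placebo samples are assayed. Placebo is a secondary matter.

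**Conclusion.** The point holds as a limited improvement to a supportive safety analysis. The status rule in SAP 3.9 cannot separate a man with unchanged pre-dose reactivity from one who seroconverts on treatment, although the pre-dose sample and titer needed to do so are planned. The effect is confined to the tables and models split by antibody status; the primary and key secondary BMD tests are untouched.

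The size is unknown. It is nil if no man is positive on Day 1. The bounds of 9% to 34% and 2% to 10% rest on rates assumed for illustration, on all 150 men having usable Day 1 and post-baseline samples, and on every Day 1 positive persisting without a titer rise. The 34% is the extreme corner of that grid and should not be quoted as an expected value.

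**What to change.** In SAP 3.9 and 4.5.4:

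1. Define treatment-emergent antibody as Day 1 negative and later positive (induced), or Day 1 positive with a prespecified rise in titer (boosted). State how a man with no Day 1 result is classed.
2. Make treatment-emergent status the main split in the analyses by antibody status, and carry it through to the neutralising-antibody columns.
3. Show Day 1 positives without a titer rise as a separate row, and state how they enter the MMRM comparison. One option is to exclude them from both groups and keep the present split on any post-baseline positive as a sensitivity analysis.
4. Add a Day 1 to post-baseline shift table.
5. If placebo samples have been assayed, tabulate them by visit as background; if not, say that they are not tested.

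Items 1 to 4 need wording and programming but no new visits or samples. The price is that the titer-rise threshold is a convention and a few men change group. Tabulating placebo costs little if results exist, and item 5 does not ask for new assay runs if they do not.
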